#### 10 INVESTIGATIONAL PRODUCTS

All participants will receive the interventions as scheduled for their allocated group, as detailed in section 3. The term 'investigational products' applies to either ChAdOx1 NipahB or 0.9% saline placebo in this study.

#### 10.1 ChAdOx1 NipahB

ChAdOx1 NipahB has been formulated and vialed under Good Manufacturing Practice conditions at the Clinical Biomanufacturing Facility (CBF), University of Oxford. At the CBF the vaccine will be certified and labelled for the trial by a Qualified Person (QP) before transfer to the clinical site. The vaccine is supplied as a liquid in glass vials for intramuscular administration and will be stored at nominal -80°C in a secure freezer at the clinical site.

Batch number NI22A23A (used for this trial) is presented in formulation buffer (10 mM Histidine, 7.5% (w/v) sucrose, 35 mM NaCl, 1 mM MgCl2, 0.1% (w/v) PS80, 0.1 mM Edetate Disodium, 0.5% (v/v) ethanol, pH 6.6). The appearance of ChAdOx1 Nipah is a slightly opaque frozen liquid, essentially free from visible particulates.

The dose of ChAdOx1 NipahB to be used in trial will be  $5 \times 10^{10}$  virus particles per administration.

# 10.2 Saline Placebo (0.9% Sodium Chloride)

The placebo consists of 0.9% sodium chloride for injection acquired from an appropriate commercial medical supplier which will be stored in accordance with manufacturer's instructions.

#### 10.3 Blinding of IMPs

ChAdOx1 NipahB and saline placebo will not be supplied to the clinical site in a blinded form. Instead, to maintain blinding they will be drawn up and prepared by unblinded staff out of sight of participants and blinded study staff. As ChAdOx1 NipahB and 0.9% sodium chloride have a potentially different appearance, vaccine syringes will be obscured using an opaque covering. The administration equipment will have the same appearance and the same volume will be used for both ChAdOx1 NipahB and placebo.

#### 10.4 Storage of ChAdOx1 NipahB

ChAdOx1 NipahB requires storage in a freezer at -70°C to -85°C and will be transported to the study site(s) after authorised release for use in the clinical trial by the CBF Qualified Person (QP) and study approval by REC and MHRA. Movements of study medication between CBF and the study site(s) will be documented in accordance with relevant SOPs.

Throughout the study, the study vaccine will be stored in temperature monitored freezers with an auditable temperature record in accordance with the manufacturer's instructions and relevant SOPs. Study freezers are connected to a monitoring system with 24-hour access to staff that are able to move the product in the event of significant temperature deviation.

#### 10.5 Compliance with Trial Treatment

The study investigational product and placebo will be administered by trained unblinded study personnel and will be documented according to GCP guidelines and relevant SOPs. Issues related to

RECRef: 23/SC/0268 NIV001: A study of a new vaccine against Nipah Page 40 of 71 IRAS project ID: 1007433 Virus in adults aged 18 to 55

Virus in adults aged 18 to 55 Protocol V4.0, 16 AUG 2024 compliance are therefore the responsibility of study personnel who have received appropriate training.

## 10.6 Accountability of The Trial Treatment

The ChAdOx1 NipahB vaccine will be manufactured, packaged, labelled and supplied by CBF. All vaccines (vials and boxes) are labelled with a label specifying 'for clinical trial use only'.

The vaccine will be delivered and stored at the study site(s) pending authorised release for use in the clinical trial.

#### 10.7 Concomitant Medication

The use of all concomitant medication prescribed or over-the-counter, will be recorded in the eCRF. Concomitant medication that will result in temporary exclusion or withdrawal of volunteers from further vaccination are detailed in section 8.2. There is otherwise no restriction on the use of concomitant medication.

# 10.8 Emergency Medication and Procedures

All clinical staff are trained and can provide evidence of competency in the acute management of anaphylaxis reactions including the use of intra-muscular adrenaline. This is detailed in relevant site SOPs and adrenaline is available at all times of vaccine administration and subsequent observation.

#### 10.9 Post-Trial Treatment

Study IMP will not be continued beyond the trial period.

## 10.10 Other Treatments (non-IMPs)

No other treatments other than those specified in the protocol above will be administered to trial participants.

#### 10.11 Other Interventions

No other interventions other than those specified in the protocol above will be administered to trial participants.

# 11 SAFETY REPORTING

# 11.1 Adverse Event Definitions

Adverse Event (AE)	Any untoward medical occurrence in a participant to whom a medicinal product has been administered, including occurrences which are not necessarily caused by or related to that product.
Adverse Reaction (AR)	An untoward and unintended response in a participant to an investigational medicinal product which is related to any dose administered to that participant.  The phrase "response to an investigational medicinal product" means that a causal relationship between a trial medication and an AE is at least a reasonable possibility, i.e. the relationship cannot be ruled out.

RECRef: 23/SC/0268 NIV001: A study of a new vaccine against Nipah Page 41 of 71

	All cases judged by either the reporting medically qualified professional or the Sponsor as having a reasonable suspected causal relationship to the trial medication qualify as adverse reactions.
Serious Adverse Event (SAE)	
 
A serious adverse event is any untoward medical occurrence that:
 
Results in death,
 
Is life-threatening,
 
Requires inpatient hospitalisation or prolongation of existing hospitalization,
 
Results in persistent or significant disability/incapacity, or
 
Consists of a congenital anomaly or birth defect.
 
Other 'important medical events' may also be considered a serious adverse event when, based upon appropriate medical judgement, the event may jeopardise the participant and may require medical or surgical intervention to prevent one of the outcomes listed above.
 
NOTE: The term "life-threatening" in the definition of "serious" refers to an event in which the participant was at risk of death at the time of the event; it does not refer to an event which hypothetically might have caused death if it were more severe.
 

Serious Adverse Reaction (SAR)	An adverse event that is both serious and, in the opinion of the reporting Investigator, believed with reasonable probability to be due to one of the trial treatments, based on the information provided.
Suspected Unexpected Serious Adverse Reaction (SUSAR)	
 
A serious adverse reaction, the nature and severity of which is not consistent with the Reference Safety Information for the medicinal product in question set out:         
 
In the case of a product with a marketing authorisation, in the approved summary of product characteristics (SmPC) for that product, or
 
In the case of any other investigational medicinal product, in the approved Investigator's Brochure (IB) relating to the trial in question.
 
 
 

NOTE: to avoid confusion or misunderstanding of the difference between the terms "serious" and "severe", the following note of clarification is provided: "Severe" is often used to describe intensity of a specific event, which may be of relatively minor medical significance. "Seriousness" is the regulatory definition supplied above.

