# 11.3 Causality Assessment

The relationship of each adverse event to the trial vaccine or study procedures must be determined by a PI-delegated blinded clinician / Investigator. The relationship of the adverse event with the study procedures will be categorized as not related, possibly related, probably related or definitely related.

RECRef: 23/SC/0268 NIV001: A study of a new vaccine against Nipah Page 43 of 71

The delegated clinician will use clinical judgement to determine the relationship using the following definitions (Table 6):

Table 6 Guidelines for assessing the relationship of vaccine administration to an Adverse Event

No Relationship		No temporal relationship to study product; and Alternate aetiology (clinical state, environmental or other interventions); and Does not follow known pattern of response to study product.	
Related	Possible	Reasonable temporal relationship to study product; or Event not readily produced by clinical state, environmental or other interventions; or Similar pattern of response to that seen with other vaccines.	
	Probable	Reasonable temporal relationship to study product; and Event not readily produced by clinical state, environment, or other interventions; or Known pattern of response seen with other vaccines.	
Definite		Reasonable temporal relationship to study product; and Event not readily produced by clinical state, environment, or other interventions; and Known pattern of response seen with other vaccines.	

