# 11.4 Expectedness Assessment

As no expected SARs are recorded in the 'Reference Safety Information' (section 5.4 of the ChAdOx1 NipahB Investigator's Brochure), any SARs associated with ChAdOx1 NipahB will be classified as unexpected and reported as SUSARs in this trial.

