# • Unsolicited adverse events:

RECRef: 23/SC/0268 NIV001: A study of a new vaccine against Nipah Page 50 of 71

- If 2 or more participants (per dose of vaccination) experience the same grade 3
  unsolicited adverse event (including the same laboratory adverse event, excluding
  lymphopenia) that is considered possibly, probably or definitely related to
  vaccination and persists at grade 3 for >48hrs.
- A serious adverse event considered possibly, probably or definitely related to vaccination occurs.
- o Death occurs.
- o A life-threatening reaction occurs.

If a holding rule has been met, the CI on behalf of the Sponsor will inform the regulatory authority. The DSMC will be asked to review relevant safety data and provide a recommendation on further dosing. If the DSMC recommend to restart dosing, the request (with pertinent data) must be approved by the regulatory authority prior to restarting dosing. The DSMC review would consider:

- The relationship of the AE or SAE to the vaccine.
- The relationship of the AE or SAE to the vaccine dose, or other possible causes of the event.
- If appropriate, additional screening or laboratory testing for other participants to identify those who may develop similar symptoms and alterations to the current Participant Information Sheet (PIS).
- New, relevant safety information from ongoing research programs on the various components of the vaccine.

The vaccine manufacturer (CBF) will also be notified if a holding rule is activated or released. All vaccinated participants will be followed for safety until the end of their planned participation in the study or until resolution or stabilisation (if determined to be chronic sequelae) of their AEs, providing they consent to this.

In addition to these pre-defined criteria, the study can be put on hold upon advice of the DSMC, CI, Study Sponsor, Regulatory Authority or Ethical Committee(s), for any single event or combination of multiple events which they deem jeopardise the safety of the volunteers or the reliability of the data.

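### Section 11.1 sets a stricter causality test, with fewer assessors, for a serious adverse reaction than for an adverse reaction, and that test alone gates expedited SUSAR reporting

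*Protocol*

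**What the plan says.** The definitions table in Protocol 11.1 gives two causality tests.

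- **Adverse reaction (AR).** It is enough that "a causal relationship between a trial medication and an AE is at least a reasonable possibility, i.e. the relationship cannot be ruled out". On who decides: "All cases judged by either the reporting medically qualified professional or the Sponsor as having a reasonable suspected causal relationship" qualify.
- **Serious adverse reaction (SAR).** The row does not refer back to the AR row. It requires an event that is serious and, "in the opinion of the reporting Investigator, believed with reasonable probability to be due to one of the trial treatments".

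The SUSAR row builds on the SAR: "A serious adverse reaction, the nature and severity of which is not consistent with the Reference Safety Information". Section 11.4 then removes expectedness as a filter, because no SARs are listed as expected: "any SARs associated with ChAdOx1 NipahB will be classified as unexpected and reported as SUSARs in this trial". Section 11.17 sends SUSARs to the Sponsor, the ethics committee and the MHRA, within 7 days if fatal or life-threatening and within 15 days otherwise.

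Elsewhere the protocol works with a four-level scale. Section 11.3 states: "The relationship of the adverse event with the study procedures will be categorized as not related, possibly related, probably related or definitely related". Table 6 places *possible* under the heading *related*. The group holding rules in 11.24.1 use all three related levels: "A serious adverse event considered possibly, probably or definitely related to vaccination occurs". Section 11.15 gives SAE causality to the blinded investigator and mentions no Sponsor assessment.

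**The concern.** A SAR would normally be the serious subset of adverse reactions. Here it is not. The threshold rises from possibility to probability, and the Sponsor drops out as an assessor. An event can then be serious, and be an adverse reaction by the protocol's own definition, without being a serious adverse reaction.

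This matters because nothing downstream corrects it. With expectedness neutralised by 11.4, SAR status decides on its own whether a serious event enters the expedited route in 11.17. This is a first-in-human trial, and section 5.8.1 lists very rare serious reactions to a related ChAdOx1 vaccine. For a first event of that kind, causality may well be uncertain or disputed, and those are the events on which the two rows disagree. The same term also governs unblinding by the Chief Investigator (CI) in 11.15 and one of the contraindications in 8.3, so its meaning should not be left open.

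**Working it through.** No sample size, rate or error level enters this point, so there is no figure to reproduce. The check sets the definitions side by side and follows a serious event through them.

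**Step 1: the tests compared.**

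| Place | Causality threshold | Who judges |
|---|---|---|
| 11.1, AR row | Reasonable possibility, not ruled out | Reporting professional or Sponsor |
| 11.1, SAR row | Reasonable probability | Reporting investigator |
| 11.3, Table 6 | *Possible*, *probable* and *definite* all count as related | Delegated blinded clinician or investigator |
| 11.24.1, related-SAE group rule | Possible or higher | Not specified |
| 11.24.2, related-SAE individual rule | Possible or higher | Not specified |
| 11.22.1 DSMC Reviews, item 6 | Related | Not specified |

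The SAR row alone uses a probability threshold.

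**Step 2: the chain to expedited reporting.** 11.17 applies to SUSARs. A SUSAR must first be a SAR (11.1). Every vaccine-associated SAR is unexpected (11.4). For the vaccine, SUSAR status therefore reduces to SAR status.

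**Step 3: three serious events, read literally.**

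| Event | AR? | SAR? | SUSAR route in 11.17? |
|---|---|---|---|
| (a) Investigator: possibly related, short of reasonable probability | Yes | No | No |
| (b) Investigator: not related; Sponsor suspects a link | Yes | No | No |
| (c) Investigator: at least reasonably probable | Yes | Yes | Yes |

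Cases (a) and (b) are the gap.

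**Step 4: how wide is category (a)?** In Table 6, *possible* needs only one of three conditions, joined by *or*, and a reasonable temporal relationship alone suffices. *No relationship* needs all three of its conditions, joined by *and*. An uncertain event soon after vaccination therefore tends to land in *possible*. Section 11.12 also counts any Grade 4 laboratory event as an SAE, which enlarges the pool.

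**Step 5: what else catches these events?** Case (a) meets the group holding rule. The CI then informs the regulatory authority, the DSMC reviews, and a restart needs regulatory approval (11.24.1); 11.22.1 item 6 also calls for independent review. For case (b), every SAE reaches the CI within 24 hours and the DSMC reviews SAEs (11.15), and 11.24.1 lets the Sponsor advise a hold for any single event. None of these provisions states that case (b) is reported on the 11.17 timetable.

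**Step 6: the same mismatch elsewhere.** Section 8.3 bars further vaccination after a SAR. Section 11.24.2 withdraws a participant from further vaccination after an SAE that is at least possibly related. On the literal SAR definition these are different sets of events.

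**The case against.** The strongest reply is that this is loose wording rather than an exclusion. No sentence says that a possibly related SAE is not a SAR, and nothing equates reasonable probability in 11.1 with the *probable* level of Table 6. Staff working from Table 6 may treat any *related* rating as sufficient, and the SUSAR row can be read as an adverse reaction that happens to be serious. This stands as a limit: the gap depends on reading the SAR row as written. It does not remove the point, because *possible* and *probable* are separate formal categories in this protocol, and the related-SAE holding rules name all three levels where all three are meant.

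A reader might infer that a possibly related SAE could stop dosing without the regulator hearing of it. The documents do not support that, since meeting a holding rule itself requires telling the regulatory authority. What the rule lacks is a deadline and any mention of the ethics committee. Section 13.1.4 does require notice to the MHRA and ethics committee within 15 days if the study is halted. If a dosing hold counts as a halt, the gap narrows. But that sentence sits under early termination, runs from the halt, and has no 7-day limit for fatal or life-threatening events.

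A reader might also infer that a Sponsor judgement has no effect on serious events, or that 11.15 classes such an event as unrelated. Neither is stated. The Sponsor can advise a hold, the related-SAE holding and DSMC review provisions do not say whose opinion counts, and 11.15 does not say that the investigator's view overrides the Sponsor's.

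**Conclusion.** The point holds as an internal inconsistency in the safety definitions. The SAR row is out of line with the AR row, Table 6 and the holding rules, and it is the only gate to 11.17. Read literally, one of the three related levels, and any serious event on which only the Sponsor suspects a link, falls outside the 7- and 15-day reports to the MHRA and ethics committee.

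The practical loss is limited. For the possibly related event, it is the expedited timetable and the individual report to the ethics committee, not awareness by the regulator or DSMC. For the Sponsor-only event, it is the absence of any stated expedited route. The conclusion assumes that reasonable probability is read as a higher bar than *possible*, which the wording suggests but does not spell out. How many events would be affected cannot be derived from the document. No endpoint, analysis or sample size is touched. It is worth correcting because the events concerned would be serious and first-in-human, and the correction needs only the protocol's own definitions.

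**What to change.** For safety reporting, define a SAR in 11.1 as an adverse reaction, as set out in the AR row, that meets a criterion for serious. Use that term unchanged in 11.4, 11.15 and 11.17. In 11.15, limit unrelated SAEs to those that neither the investigator nor the Sponsor judges related.

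Sections 8.3 and 11.24.2 must be reconciled explicitly. Changing the definition in 11.1 would alter what 8.3 covers, and that should not happen as a side effect. Which trigger should govern further vaccination is for the sponsor to settle.

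The cost is wording, with no change to visits or analyses. There would be some more expedited reports. There may also be more unblinding, because 11.15 makes the CI, otherwise blinded under 7.5, responsible for unblinding in the event of a SAR. Section 7.5 already allows unblinding for any SAE after discussion with the CI or DSMC, so this extends an existing possibility. The document gives no basis for putting a number on either.

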# 11.2 Adverse Events of Special Interest (AESI)

AESIs will be monitored and recorded throughout the study period. These will include the list below (Table 5). Additionally, other adverse events (i.e. not listed below) may also be categorised by investigators as AESIs if scientifically warranted.

RECRef: 23/SC/0268 NIV001: A study of a new vaccine against Nipah Page 42 of 71 IRAS project ID: 1007433 Virus in adults aged 18 to 55

Table 5 List of Adverse Events of Special Interest (AESIs)

Respiratory	Acute Respiratory Distress Syndrome (ARDS)
	Pneumonitis
Neurological	Transverse Myelitis
	Generalised convulsion
	Guillain-Barre Syndrome (GBS)
	Acute Disseminated Encephalomyelitis (ADEM)
	Encephalopathy
	Encephalitis / encephalomyelitis
	Aseptic meningitis
	Stroke
Haematological / Vascular	Thrombocytopenia
	Thrombosis with Thrombocytopenia Syndrome (TTS)
	Major thrombosis (without thrombocytopenia)
	Heparin-Induced Thrombocytopenia (HIT)
	Immune thrombocytopenic purpura (ITP)
	Disseminated intravascular coagulation (DIC)
Immunological	Anaphylaxis
	Vasculitis
	Capillary Leak Syndrome (CLS)
	Other Immune-Mediated Conditions
Other	Acute renal failure
	Serious injection site reaction, such as ulceration, abscess or necrosis

# 11.3 Causality Assessment

The relationship of each adverse event to the trial vaccine or study procedures must be determined by a PI-delegated blinded clinician / Investigator. The relationship of the adverse event with the study procedures will be categorized as not related, possibly related, probably related or definitely related.

RECRef: 23/SC/0268 NIV001: A study of a new vaccine against Nipah Page 43 of 71

The delegated clinician will use clinical judgement to determine the relationship using the following definitions (Table 6):

Table 6 Guidelines for assessing the relationship of vaccine administration to an Adverse Event

No Relationship		No temporal relationship to study product; and Alternate aetiology (clinical state, environmental or other interventions); and Does not follow known pattern of response to study product.	
Related	Possible	Reasonable temporal relationship to study product; or Event not readily produced by clinical state, environmental or other interventions; or Similar pattern of response to that seen with other vaccines.	
	Probable	Reasonable temporal relationship to study product; and Event not readily produced by clinical state, environment, or other interventions; or Known pattern of response seen with other vaccines.	
Definite		Reasonable temporal relationship to study product; and Event not readily produced by clinical state, environment, or other interventions; and Known pattern of response seen with other vaccines.	

# 11.4 Expectedness Assessment

As no expected SARs are recorded in the 'Reference Safety Information' (section 5.4 of the ChAdOx1 NipahB Investigator's Brochure), any SARs associated with ChAdOx1 NipahB will be classified as unexpected and reported as SUSARs in this trial.

# 11.5 Severity Assessment

The severity of clinical and laboratory adverse events will be assessed according to scales based on FDA toxicity grading scales for healthy volunteers enrolled in preventive vaccine clinical trials. Laboratory adverse event severity gradings will be used; they are listed in Appendix B: Severity Grading Scales.

